## **6. Investigational Plan**

**6.1 Visit Schedule / Clinical Data Collection.** No additional procedures or assessments will be mandated for study participants. Standard clinical assessments and data will be collected. This will include baseline National Institutes of Health Stroke Scale NIHSS, Glasgow Coma Scale (GCS) and vital signs, which will be recorded in a case report form. Stroke risk factors, past medical history and medications, baseline complete blood count, coagulation profile and renal function tests will also be recorded. CHADS2 and CHADSVaSC scores will also be recorded. Clinical endpoints will be ischemic stroke or intracranial hemorrhage within 30 days of anticoagulant initiation. All cerebral ischemic and intracranial hemorrhagic endpoints will be centrally adjudicated from anonymized clinical records, with the intracranial hemorrhages classified as described above. A data collection form will be filled out for each subject at 30 days post-enrolment indicating clinical status and occurrence of outcome events.

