**Study Procedures:**

This is a phase IV registry study. No additional procedures are included in the study. Standard clinical data will be collected. This will include a physical examination and NIHSS score assessment at baseline.

In addition, all neuro-imaging will be collected. Standard imaging includes a non-contrast CT brain at baseline and 7±2 days post-treatment.

Repeat NIHSS score assessment at the time of the 7 day CT scan.

Repeat clinical and NIHSS score assessment 30 days post-enrolment will also be collected when performed as part of standard care.

**Safety  
Parameters/analysis:**

An independent DSMB will be sent blinded outcome data, including all cases with symptomatic or asymptomatic parenchymal haemorrhage. The DSMB will review adverse events after every 100 patients recruited.

**Imaging  
Parameters/Analysis**

All imaging data collected as part of standard care will be sent to the core imaging lab for analysis.

**Image Analysis.** Dicom CT data will be transferred to the Stroke Imaging Laboratory at the University of Alberta for post-processing and analysis. All image assessments will be performed using the Quantomo software package (Cybertrial Inc, Calgary, AB).

All cases of hemorrhagic transformation seen on day 7 scans will be graded using the ECASS (European Cooperative Acute Stroke Study) hemorrhage classification scheme:

1. PH2 - parenchymal hemorrhage as a blood clot in more than 30% of the infarcted area with substantial space-

- occupying effect.
2. PH1 - parenchymal hemorrhage as blood clots in 30% or less of the infarcted area with some slight space-occupying effect.
  3. HT2 - hemorrhagic transformation 2 - confluent petechiae within the infarcted area but no space-occupying effect.
  4. HT1 - hemorrhagic transformation 1 – small petechiae along the margins of the infarct.
  5. R - remote ICH, i.e. not topographically related to the infarct (most often in the contralateral hemisphere).

*A symptomatic ICH will be defined as PH2, associated with an NIHSS deterioration of  $\geq 4$  points.*

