## **5. Variables and Assessment.**

**5.1.1 Effectiveness.** This is a registry of the safety of early anticoagulation (see 5.2). A measure of the effect of early anticoagulation will be assessed; the rate of new ischemic stroke/TIA occurrence within the 30-day study period will be recorded. It is recognized that the event rate will be low and the study is neither designed, nor powered to demonstrate a decrease in early ischemic stroke rates.

**5.1.2 Primary Outcome (Safety).** The primary study outcome measure is the symptomatic hemorrhagic transformation rate (PH2 associated with clinical deterioration, defined as worsening of NIHSS score of 4 or more points, within 30 days of initiating dabigatran therapy).

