## **7. Statistical Methods and Sample Size**

**7.1 Statistical Analysis and Sample Size Considerations:** The registry will include 500 patients. This sample size is considered adequate to ensure inclusion of a significant number of patients treated at a range of time points within the post-stroke period. The primary analysis will be done on an Intention

To Treat basis. We will also complete a sensitivity analysis on individuals who discontinued dabigatran treatment and/or switched to other antithrombotic agents. Based on the inclusion/exclusion criteria, there will not be any individuals taking dabigatran concomitantly with other antithrombotic drugs.

The primary and secondary outcomes will be defined with descriptive statistics. The rate of PH2 (and all other forms of hemorrhagic transformation) will be defined as a ratio (%) of the total number of patients enrolled in the study (ITT analysis).

The primary stratification variable is warfarin use prior to the TIA/minor stroke. The secondary strata are 1. Dabigatran dose (150 mg BID versus 110 mg BID) and 2. Time to initiation of therapy (0-2 days, 3-7 days and > 7 days). All results including baseline patient characteristics will be stratified by use of warfarin prior to the event and by the dabigatran dose after the event as described in **appendices 2-4**.

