**Limitations.** There are recognized limitations to this study. The eligibility criteria are consistent with a low risk population, and the results of this study will not be generalizable to other, higher risk stroke/TIA populations. Even in the population of TIA and minor stroke patients, the time between symptom onset and treatment initiation may vary with the severity of the clinical presentation. Although it is not our intention, clinicians may be more likely to initiate therapy earlier in patients with complete resolution of all neurological deficits. Only dabigatran treated patients will be included in this registry. Unintended selection bias may also arise from survival bias over the time from incident stroke/TIA to time of dabigatran treatment and start of follow-up. Finally this is a small (500) single arm study with a relatively short (30 day) follow-up period. This short time period will permit assessment of the most important safety variable (hemorrhagic transformation rates). It will also minimize loss to follow-up. Although functional outcome is generally assessed at 90 days, this pilot study is too small to adequately assess that endpoint.

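### A 30-day outcome form is due for every patient, but no day-30 contact, source or unknown-status rule is set; with all enrolled as denominator, hemorrhagic transformation rates may be understated

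*Combined protocol and SAP*

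**What the plan says.** Four parts of the protocol bear on this.

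- **The form.** Section 6.1: "A data collection form will be filled out for each subject at 30 days post-enrolment indicating clinical status and occurrence of outcome events".
- **What is required of sites.** The same section opens with "No additional procedures or assessments will be mandated for study participants". The synopsis, under Study Procedures, says of day 30: "Repeat clinical and NIHSS score assessment 30 days post-enrolment will also be collected when performed as part of standard care".
- **The outcome.** Section 5.1.2 defines the primary outcome as PH2 with "worsening of NIHSS score of 4 or more points, within 30 days of initiating dabigatran therapy". A patient's status on it therefore has to be known for the whole 30 days.
- **The denominator.** Section 7.1 states "The registry will include 500 patients" and says that the rate of PH2, and of all other forms of HT, "will be defined as a ratio (%) of the total number of patients enrolled in the study (ITT analysis"). Its only sensitivity analysis concerns patients who stop dabigatran or switch drug. There is no missing-data rule.

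No section names the source of the 30-day form or requires a visit, call or record check to complete it. None says what to do when status is not known. The outcome table in Appendix 4 has no entry for unknown status. The Limitations paragraph says of the short follow-up period: "It will also minimize loss to follow-up". No expected or tolerated rate of loss is given.

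**The concern.** The plan cannot tell a patient without an event from a patient without information. In the HT rates both sit in the denominator, and neither can enter the numerator.

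This matters because the study has a single arm, and section 3.1 rests its safety conclusion on hemorrhage rates being low. Missed events push the result toward that conclusion, and no control group shares the error. The patients have TIA or minor stroke, and section 6.2.2 expects some to start treatment as outpatients or in the Emergency Department, so it cannot be assumed that the site will see every patient again. Few events are expected, so a single missed one would be visible in the rate. Objective 3 in section 2.2 also needs neurological outcome at 30 days, which the plan collects only where usual care supplies it.

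**Working it through.** **The plan's own figure.** Section 2.3 takes 1.7% for symptomatic HT on heparin and applies a ratio of 1/3: 1.7% × 1/3 = 0.567%, which rounds to the stated 0.6%. In 500 patients that is 500 × 0.006 = 3 events. The sample size of 500 has no calculation behind it to check.

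**Inputs.** True rate p = 0.6% (section 2.3); N = 500 (section 7.1). The documents do not give the share m of patients whose status is unascertained, so 10–30% is an assumption. The share c of those patients' events found by another route is not given either, so the full range 0 to 1 is shown.

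**Expected reported rate over all enrolled**, with equal risk in ascertained and unascertained patients: p × [(1 − m) + m × c]. The relative bias is −m(1 − c).

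| m | c = 0 | c = 0.5 | c = 1 |
|---|---|---|---|
| 10% | 0.54% (2.70 events) | 0.57% | 0.60% |
| 20% | 0.48% (2.40 events) | 0.54% | 0.60% |
| 30% | 0.42% (2.10 events) | 0.51% | 0.60% |

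The c = 0 column assumes that every event in these patients is missed over the full 30 days. The CT at 7±2 days should find some early ones, so for equal risk this column is the outer end of the range.

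**Chance that any event falls among the unascertained**, 1 − (1 − 0.006)^(500m): 26% for 50 patients, 45% for 100 and 59% for 150.

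**Precision with no events observed.** The exact two-sided 95% upper limit is 1 − 0.025^(1/n). It is 0.74% for n = 500, and 0.82%, 0.92% and 1.05% for n = 450, 400 and 350 patients with known status. With 3 observed events, 3/500 = 0.60% has an upper limit of 1.74%. The known-status figures are 3/450 = 0.67% (1.94%), 3/400 = 0.75% (2.18%) and 3/350 = 0.86% (2.48%).

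**If risk differs.** Suppose the unascertained have twice the risk, the overall rate is still 0.6%, and c = 0. The rate in the ascertained is then 0.6%/[(1 − m) + 2m], or 0.55% at m = 10% and 0.50% at m = 20%. The all-enrolled rate is that times (1 − m), or 0.49% and 0.40%. Changing the denominator does not remove this part of the bias, so the number with unknown status has to be reported as well.

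**Other outcomes.** The all-enrolled denominator in section 7.1 is stated for PH2 and other HT only. None is stated for recurrent stroke/TIA or systemic hemorrhage, so the table applies to them only if all enrolled patients are used there too.

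**The case against.** A reader might infer that patients not seen at day 30 are entered on the form as event-free, and that the 30-day rates are therefore biased low. The documents do not support either as a fact. A form required for each subject can be read as a duty to find out, by call, clinic letter or record check, and declining to mandate assessments does not rule out a call. The 30-day form is not reproduced (Appendix 1 lists baseline items only), so it may already carry an unknown code.

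There are also other routes to an event:

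- Serious adverse events are reported for a month plus a margin. The margin is three days in section 5.2.2 and seven in 6.2.2, which must be reconciled.
- Section 5.2.3 calls for an immediate CT on deterioration and collects any brain imaging within 30 days.
- Section 6.1 has ischemic and intracranial hemorrhagic endpoints adjudicated centrally from clinical records.
- Exclusion criterion 8 screens out patients unlikely to comply with follow-up.

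PH2 with a worsening of 4 or more NIHSS points is the outcome least likely to escape these routes. The study is descriptive and, by section 7.2, hypothesis-generating. The remark on loss to follow-up explains the short period and claims no achieved rate.

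Most of this stands and limits the claim, but it does not close the gap. Safety reports and CT on deterioration work only if the event reaches the site. Adjudication classifies events already found and does not cover systemic bleeding. The exclusion criterion ascertains no one. However the form is filled in, the denominator rule counts an unknown status as a non-event in the HT rates.

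**Conclusion.** The point holds as a gap in ascertainment and analysis. No day-30 contact is required, no source or unknown status is specified, and the stated denominator makes unascertained patients non-events for PH2 and all other HT. The HT rates may be understated. Missed events can only lower the all-enrolled rate, but the amount is not known and is zero if every event surfaces by another route.

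The illustration of 0.54–0.42% against a true 0.6% rests on an assumed 10–30% unascertained, equal risk and no capture elsewhere. The rise in the zero-event upper limit from 0.74% to 0.82–1.05% rests on the same assumed shares and ignores the partial follow-up of the unascertained. It would be tempting to extend these figures to recurrent stroke/TIA and systemic bleeding, but the plan states no denominator there. The change should be made; the gap does not invalidate the registry.

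**What to change.** **Section 6.1.** Have the 30-day form record the source of information (visit, telephone, record review, none) and the date the patient was last known to be event-free. Allow unknown for each outcome. A calendar date also lets follow-up be counted from the first dose, as section 5.1.2 requires, although the form itself is timed from enrolment.

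**Section 7.1.** Report the number with unknown 30-day status. Keep the all-enrolled rate, labelled as a lower bound, and beside it give the 30-day cumulative incidence of each clinical outcome, censored at the last-known date. Censoring assumes that later risk is the same in those censored and those followed, and the text should say so. A rate among patients with known status may be added as a sensitivity analysis. It can overstate the rate if events become known more readily than event-free status, because it drops the event-free patients whose status is unknown. Censoring reduces that problem, since those patients still contribute the days for which they are known, but does not remove it. State the denominator for recurrent stroke/TIA and systemic hemorrhage.

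**Cost.** A few form fields, one more column in the outcome table, and possibly slightly less favourable rates. No visit or procedure is added. If follow-up proves nearly complete, the figures will barely differ, and the registry will be able to show that loss was small.

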### **6.2 Details of Study Procedures**

**6.2.1 Screening and run-in procedures.** NA.

**6.2.2 Treatment Period.** Patients will be treated long-term with dabigatran if deemed appropriate by the attending physician and the patient is in agreement. The study outcome event period is 30 days from drug initiation. The SAE reporting period is an additional 7 days.

The time from symptom onset to dabigatran initiation will be recorded in the CRF. In all cases, dabigatran will be prescribed by a stroke neurologist participating in the registry. The location of the patient at the time of dabigatran initiation will be recorded (inpatient/outpatient/Emergency Department).

**6.2.3. End of Trial and follow-up.** The registry data collection period will be complete after 30 days.

## **7. Statistical Methods and Sample Size**

**7.1 Statistical Analysis and Sample Size Considerations:** The registry will include 500 patients. This sample size is considered adequate to ensure inclusion of a significant number of patients treated at a range of time points within the post-stroke period. The primary analysis will be done on an Intention

To Treat basis. We will also complete a sensitivity analysis on individuals who discontinued dabigatran treatment and/or switched to other antithrombotic agents. Based on the inclusion/exclusion criteria, there will not be any individuals taking dabigatran concomitantly with other antithrombotic drugs.

The primary and secondary outcomes will be defined with descriptive statistics. The rate of PH2 (and all other forms of hemorrhagic transformation) will be defined as a ratio (%) of the total number of patients enrolled in the study (ITT analysis).

The primary stratification variable is warfarin use prior to the TIA/minor stroke. The secondary strata are 1. Dabigatran dose (150 mg BID versus 110 mg BID) and 2. Time to initiation of therapy (0-2 days, 3-7 days and > 7 days). All results including baseline patient characteristics will be stratified by use of warfarin prior to the event and by the dabigatran dose after the event as described in **appendices 2-4**.

**Limitations.** There are recognized limitations to this study. The eligibility criteria are consistent with a low risk population, and the results of this study will not be generalizable to other, higher risk stroke/TIA populations. Even in the population of TIA and minor stroke patients, the time between symptom onset and treatment initiation may vary with the severity of the clinical presentation. Although it is not our intention, clinicians may be more likely to initiate therapy earlier in patients with complete resolution of all neurological deficits. Only dabigatran treated patients will be included in this registry. Unintended selection bias may also arise from survival bias over the time from incident stroke/TIA to time of dabigatran treatment and start of follow-up. Finally this is a small (500) single arm study with a relatively short (30 day) follow-up period. This short time period will permit assessment of the most important safety variable (hemorrhagic transformation rates). It will also minimize loss to follow-up. Although functional outcome is generally assessed at 90 days, this pilot study is too small to adequately assess that endpoint.

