## Synopsis

**Study Title:** Canadian Pradaxa Acute Stroke Safety Study (CPASS)

**Protocol Number:** CSC2012-01

**Development Phase:** Phase IV Registry

**Indication:** Minor Stroke (NIHSS Score  $\leq 3$ ) and Transient Ischemic Attack Patients with a known history of or demonstrated atrial fibrillation (paroxysmal or persistent), who can be treated with dabigatran following stroke.

**Study Drugs:  
(Including test,  
comparator, dosage  
form, dosing regimen  
and route)** Dabigatran Etxilate  
Dose: 150 mg PO BID OR 110 mg PO BID (dose determined by patient age and renal function)  
Route: PO  
  
Comparator : None (open label, single arm trial)

**No. Subjects:** 500

**No. Centres:** 15 centres within Canada

**Study Duration:** 2 years. Patients will participate in the trial for 1 month.

**Objectives of the Study:** The primary aim of the CPASS registry is to demonstrate the safety of early anticoagulation with dabigatran following cardioembolic stroke. Safety will be established by demonstrating low rates of hemorrhage in this setting.

**Study Endpoints:  
(Primary and  
Secondary)** *Primary Outcome*  
Symptomatic Hemorrhagic Transformation Rate (PH2) associated with clinical deterioration, defined as worsening of NIHSS score of 4 or more points within 30 days of initiating dabigatran therapy.

*Secondary Outcomes*  
Any parenchymal haemorrhage (PH1 or PH2) on follow-up CT scan at 7 $\pm$ 2 days post-enrolment

Symptomatic hemorrhagic transformation rate (defined as above) in patients treated with warfarin prior to the index stroke/TIA.

Recurrent TIA/Ischemic Stroke within 30 days of enrolment  
 Systemic hemorrhagic complication rate within 30 days of enrolment

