### **5.1.2 Secondary Outcomes.**

The rate of any objective hemorrhagic transformation on the day 7 post-dabigatran initiation non-contrast CT scan.

The rate of secondary hemorrhagic transformation in patients taking warfarin prior to the stroke/TIA.

The rate of hemorrhagic transformation in patients started on dabigatran within 7 days of stroke/TIA versus those started >7 days after symptom onset. Recurrent TIA/Ischemic Stroke within 30 days of dabigatran initiation.

Systemic hemorrhagic complication rate within 30 days of dabigatran initiation.

The rate of hemorrhagic transformation in patients started on dabigatran within 7 days of stroke/TIA versus those started >7 days after symptom onset.

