### **5.2.3 Assessment of safety laboratory parameters.**

**Imaging Data Collection.** No additional imaging will be required for study participants. Only standard clinical data will be collected. Acute baseline CT scans will be collected. Dicom files will be transferred to a central imaging database. All patients will have a follow-up non-contrast CT scan  $7\pm 2$  days after enrolment, in order to assess for early asymptomatic hemorrhagic transformation. In the event of any clinical deterioration, a repeat CT scan will be performed immediately. In addition, any supplemental brain imaging completed within the first 30 days after enrolment will be collected.

**Image Analysis.** Dicom CT data will be transferred to the Stroke Imaging Laboratory at the University of Alberta for post-processing and analysis. All image assessments will be performed using software developed specifically for CT brain image analysis (Quantomo software package, Cybertrial Inc, Calgary, AB). The extent of any objective acute and chronic ischemic changes on all CT scans will be

assessed using Alberta Stroke Program Early CT Scores (ASPECTS). It is expected baseline scans will not have evidence of acute ischemic changes, but this will be verified centrally. The extent of periventricular leukoariosis will also be measured using planimetric techniques and an intensity threshold algorithm included in the Quantomo software package.

All cases of hemorrhagic transformation seen on post-dabigatran treatment scans will be graded using the ECASS (European Cooperative Acute Stroke Study) hemorrhage classification scheme:

6. PH2 - parenchymal hemorrhage as a blood clot in more than 30% of the infarcted area with substantial space-occupying effect.
7. PH1 - parenchymal hemorrhage as blood clots in 30% or less of the infarcted area with some slight space-occupying effect.
8. HT2 - hemorrhagic transformation 2 - confluent petechiae within the infarcted area but no space-occupying effect.
9. HT1 - hemorrhagic transformation 1 – small petechiae along the margins of the infarct.
10. R - remote ICH, i.e. not topographically related to the infarct (most often in the contralateral hemisphere).

*A symptomatic ICH will be defined as PH2, associated with an NIHSS deterioration of  $\geq 4$  points.*

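### Section 7.1 divides every form of hemorrhagic transformation (HT) by all patients enrolled and has no rule for missing follow-up imaging, so the asymptomatic and any-HT rates are understated if any unimaged patient has HT

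*Combined protocol and SAP*

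**What the plan says.** Section 7.1 sets a single denominator. The rate of PH2, and of all other grades of HT, "will be defined as a ratio (%) of the total number of patients enrolled in the study (ITT analysis". The only sensitivity analysis planned there is a "sensitivity analysis on individuals who discontinued dabigatran treatment and/or switched to other antithrombotic agents". No section gives a rule for a missed, out-of-window or unreadable scan, or defines a set of patients with evaluable imaging.

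Two results depend on imaging. Section 2.2 makes the frequency of asymptomatic HT an objective. Section 5.1.2 (Secondary Outcomes) lists "The rate of any objective hemorrhagic transformation on the day 7 post-dabigatran initiation non-contrast CT scan".

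On whether the scan takes place:
- Synopsis, Study Procedures: "Standard imaging includes a non-contrast CT brain at baseline and 7±2 days post-treatment".
- Section 5.2.3: "All patients will have a follow-up non-contrast CT scan" about a week after enrolment. The same paragraph opens by saying that the study asks for no extra imaging. It adds that any clinical deterioration leads to an immediate repeat CT, and that "any supplemental brain imaging completed within the first 30 days after enrolment will be collected".
- Section 6.1: "No additional procedures or assessments will be mandated for study participants".

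On who is counted: Section 3.3 keeps a log of everyone who consents, treated or not, but follows only those treated with dabigatran. Section 4.1 and the Limitations paragraph of Section 7.1 describe the registry as made up of dabigatran-treated patients.

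The start of the scan window varies. It is enrolment in the Synopsis outcome ("Any parenchymal haemorrhage (PH1 or PH2) on follow-up CT scan at 7"±2 days) and in Section 5.2.3, treatment in the Synopsis procedures, and dabigatran initiation in Section 5.1.2.

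**The concern.** A patient with no readable follow-up scan cannot contribute an asymptomatic HT to the numerator but stays in the denominator. Read literally, Section 7.1 counts that patient as free of HT. The ITT label does not help: it says who is analysed, not what outcome to assign when none was observed.

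The direction matters because Section 3.1 intends to establish safety by showing low hemorrhage rates in a single arm. Any error from unimaged patients runs towards that conclusion, and there is no comparator in which a similar error could offset it. A reader cannot judge its size unless the number with evaluable imaging is reported.

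The word "enrolled" adds a second, smaller ambiguity. If it were taken to include the consented but untreated patients in the Section 3.3 log, people who are never followed would dilute every rate.

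**Working it through.** **Plan's own figure.** There is none to reproduce. The documents give no expected asymptomatic or any-HT rate and no expected share of missing scans. The planned size is 500 (Section 7.1). Everything about missing imaging below is an assumption, shown over a range.

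**Notation.** m = share of treated patients with no evaluable follow-up imaging; q = HT risk in imaged patients; r = risk in unimaged divided by risk in imaged patients; D = 1 − m + m·r. HT in imaged patients is taken as fully detected.

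- True rate = q(1 − m) + q·m·r = q·D
- Section 7.1 rate = q(1 − m)
- Relative understatement of the Section 7.1 rate = 1 − (1 − m)/D = m·r/D
- Evaluable-only rate = q; its relative overstatement = 1/D − 1 = m(1 − r)/D

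The understatement does not depend on q and is never negative. It is zero if m = 0 or r = 0. Example: m = 0.10, r = 2 gives 0.20/1.10 = 18.2%.

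Relative understatement of the Section 7.1 rate:

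| Assumed m | r = 0 | r = 0.5 | r = 1 | r = 2 |
|---|---|---|---|---|
| 5% | 0% | 2.6% | 5.0% | 9.5% |
| 10% | 0% | 5.3% | 10.0% | 18.2% |
| 20% | 0% | 11.1% | 20.0% | 33.3% |

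**Which denominator is closer.** Setting m·r = m(1 − r) gives r = 0.5 for every m. Below 0.5 the all-enrolled rate is nearer the truth; above 0.5 the evaluable-only rate is nearer.

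**Illustration (assumed counts).** Take 20 HT in 400 imaged of 500 treated, with exact 95% intervals.
- All treated: 20/500 = 4.0% (2.5 to 6.1)
- Evaluable only: 20/400 = 5.0% (3.1 to 7.6)
- Allowing for the other 100 patients: (20 + 100 × r × 0.05)/500 = 4.0%, 4.5%, 5.0% and 6.0% at r = 0, 0.5, 1 and 2

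With no events, the upper 95% limit is 0.74% for 0/500 and 0.92% for 0/400.

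**Strata.** Appendix 4 tabulates asymptomatic HT in columns by prior warfarin (VKA) use and dose. Two columns with equal risk throughout, but 10% and 20% unimaged, would show a ratio of 0.90/0.80 = 1.125.

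**Primary outcome.** Section 2.3 expects 0.6%, that is 500 × 0.006 = 3 events. 3/500 = 0.60% (0.12 to 1.74). If 50 patients had unknown status (assumed), 3/450 = 0.67% (0.14 to 1.94).

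**The case against.** The strongest reply is that the problem may never arise. Section 5.2.3 says everyone is scanned and the Synopsis treats the CT as standard. A scan that is already standard care is not an additional procedure, so Section 6.1 does not show that scans will be missed. Exclusion criterion 8 removes patients not expected to comply with follow-up, and the Limitations paragraph expects the short follow-up to limit losses. Other imaging within 30 days can also recover some HT. All of this stands. A reader might infer that scans will be missing and the rates will therefore be too low; the documents support only the conditional statement. Missing scans alone are not enough either: some unimaged patients must have HT.

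A second tempting inference is that dividing by imaged patients is simply correct. It is not. Deterioration triggers a CT, so unimaged patients may well be at lower risk, and below r = 0.5 the all-enrolled rate is the better of the two.

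A third is that the primary outcome is compromised in the same way. The deterioration CT and the 30-day form for each subject (Section 6.1) make that unlikely. Ascertainment is not complete, however: central adjudication covers reported endpoints rather than every subject, and the Synopsis collects the 30-day NIHSS only when it is done in standard care.

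Nor can distortion of the Appendix 4 rows by time-to-initiation strata be claimed. Those rows are labelled by days after dabigatran initiation; only the warfarin and dose columns are open to uneven imaging.

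Finally, Section 7.2 calls the study hypothesis generating. No test is affected. But in a descriptive study the rate is the result, so its denominator has to be interpretable.

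**Conclusion.** The point holds in conditional form. Section 7.1 as written counts a patient without evaluable follow-up imaging as free of HT. If there are such patients and any of them have HT, the asymptomatic and any-HT rates are understated by a relative m·r/(1 − m + m·r), and missing imaging never overstates them. At an assumed 10% unimaged this is 0% to 18.2% for r from 0 to 2. Neither m nor r can be taken from the documents, so the actual size is unknown and may be nil. The effect is on how descriptive secondary rates are read, not on a hypothesis test. The symptomatic PH2 outcome is less exposed. The gap is worth closing because the error can run only towards the low rates on which the safety claim rests, and closing it is cheap.

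**What to change.** Amend Section 7.1:

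1. Define the denominator as patients who started dabigatran, in line with Sections 3.3 and 4.1 and the Limitations paragraph.
2. Define evaluable once: at least one readable brain scan after dabigatran initiation and within 30 days. Count HT on any such scan in the numerator, so that HT found on an early deterioration CT is not lost. Report any-HT and asymptomatic-HT rates side by side for evaluable patients and for all treated patients. Give the day 7 CT rate as a separate line with its own number scanned, after reconciling the window anchor across the Synopsis and Sections 5.1.2 and 5.2.3.
3. Tabulate the numbers treated, evaluable and with known 30-day status by prior warfarin use, dose and time to initiation.
4. Add a sensitivity analysis only for patients with no evaluable follow-up imaging, setting their risk at 0, 0.5, 1 and 2 times that of evaluable patients.

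The cost is wording and a few table rows, with no new scans, visits or data. Rates may look slightly less favourable and less precise (in the illustration, 3.1 to 7.6 against 2.5 to 6.1). The evaluable-only rate overstates if unimaged patients are at lower risk, which is why neither rate should stand alone. A patient imaged only early counts as evaluable although later HT could be missed; the separate day 7 line lets the reader see that.
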